9.1.6 Adverse Event Reporting

AEs must be recorded into the EDC system designated by the University of Virginia database, per the following guidelines.

Table 3

| | Reporting req | uirements f | or AEs that oc | Table 3: High R ccur within 30 da | | se of protocol s | pecified treatme | nt |
|----------------------------------|-------------------|-------------|----------------|--------------------------------------|----------------------|-------------------------|----------------------|---------------------|
| | Grade 1 | Grade 2 | | Grade 3 | | | | Grade 4 & 5 |
| | Expected | | | Expected | | Unexpected | | Expected |
| | and Unexpected | Expected | Unexpected | Without hospitalization | With hospitalization | Without hospitalization | With hospitalization | and Unexpected |
| Unrelated Unlikely | 30 days | 30 days | 30 days | 30 days | 15 days | 30 days | 15 days | 7 days |
| Possible Probable Definite | 30 days | 30 days | 15 days | 30 days | 15 days | 7 days | 7 days | (24-hrs)* 7 days |

^{*}Enter into Cancer Center database within 24 hours if unexpected and definitely related to protocol specified treatment Hospitalization defined as an inpatient hospital stay or prolongation of a hospital stay equal to or greater than 24 hours

9.1.7 Serious Adverse Event Reporting

The study clinician will report to the overall study PI any serious adverse event, whether or not considered study intervention related, including those listed in the protocol or clinical use instructions, and must include an assessment of whether there is a reasonable possibility that the study intervention caused the event. See Study Reference Manual for contact information and instructions for reporting.

All serious adverse events (SAEs) will be followed until satisfactory resolution or until the site investigator deems the event to be chronic or the participant is stable. Other supporting documentation of the event may be requested by the UVA Coordinating Center (UVA CC) and should be provided as soon as possible.

Site Reporting Requirements

Any Event Resulting in death that is deemed DEFINITELY related to (caused by) study participation

OR

Any event deemed serious

 Report to the UVA CC within 24 hours from the time the study team received knowledge of the event according to UVA CC requirements.

Version Date: 11/16/2021

- Non relying sites: report to your IRB in accordance with your IRB guidelines.
- Relying sites (use the UVA IRB-HSR as the IRB of record): the UVA CC will report to the UVA IRB-HSR in accordance with the guidelines.
- UVA site: report to the UVA IRB-HSR in accordance with the guidelines.

UVA Reporting Guidelines

- Notify the UVA IRB-HSR of any event resulting in death that is deemed DEFINITELY related to (caused by) study within 24 hours from the time the study team received knowledge of the event. Report using IRB Online and by telephone.
- Notify the UVA IRB-HSR of any serious, unexpected and related adverse event within 7 calendar days from the time the study team receives knowledge of the event. Timeline includes submission of signed hardcopy of AE form. Report using IRB online.
- For events considered at least possibly related to BrachyGel, notify Brachyfoam within 72 hours of UVA CC's awareness of the event. To do so, email [contact].

9.2 Unanticipated Adverse Device Effects

9.2.1 Definition of Unanticipated Adverse Device Effect (UADE)

Unanticipated adverse device effect is any serious adverse effect on health or safety or any life-threatening problem or death caused by, or associated with a device, if that effect, problem, or death was not previously identified in nature, severity, or degree of incidence in the investigational plan or application (including a supplementary plan or application), or any other unanticipated serious problem associated with a device that relates to the rights, safety, or welfare of subjects (21 CFR 812.3(s)).

9.2.2 Reporting of UADE

Site Reporting Requirements

- The study investigator shall complete an Unanticipated Adverse Device Effect
 Form and submit to the UVA CC and to the reviewing Institutional Review Board
 (IRB) according to the IRB's guidelines, but in no event later than 10 working days
 after the investigator first learns of the effect.
- Non relying sites: report to your IRB in accordance with your IRB guidelines.
- Relying sites (use the UVA IRB-HSR as the IRB of record): report to the UVA CC within 5 calendar days so that the UVA CC can report to the reviewing IRB within 10 calendar days.
- UVA site: report to the UVA CC within 5 calendar days so that the UVA CC can report to the reviewing IRB within 10 calendar days.

UVA Reporting Guidelines

 The UVA CC is responsible for conducting an evaluation of an unanticipated adverse device effect and shall report the results of such evaluation to all reviewing IRBs and participating investigators within 10 working days after the UVA CC first receives notice of the effect. Thereafter, the UVA CC shall submit such additional reports concerning the effect as the IRBs/participating investigator requests.

Version Date: 11/16/2021

- If the PI or UVA DSMC determine that an unanticipated adverse device effect
 presents an unreasonable risk to subjects shall terminate all investigations or
 parts of investigations presenting the risk as soon as possible. Termination shall
 occur not later than 5 working days after the sponsor makes this determination
 and not later than 15 working days after the UVA CC first received notice of the
 effect.
- For events considered at least possibly related to BrachyGel, notify Brachyfoam within 72 hours of UVA CC's awareness of the event. To do so, email [contact].

9.3 Reporting Events to Participants

If there is any new information relevant to the participant's willingness to continue to participate in the study, such as if there are new risks of the study treatment identified that were not included on the consent form that the participant signed, the study team will contact the participant to discuss this information. If the participant is still receiving study treatment, the study team will present the participant with an updated consent and confirm that he or she wants to continue receiving study treatment. Each site PI will determine whether new risks are applicable to participants who are in follow-up, whether participants need to be notified, and whether re-consenting is required.

9.4 Reporting of Pregnancy

Pregnancy does not need to be reported to UVA IRB-HSR. Women found to be pregnant should not receive any further brachytherapy. While the study intervention (packing system type) should not affect pregnant women or the unborn child, pregnant women should not receive radiation in this area.

9.5 Unanticipated Problems

9.5.1 Definition of Unanticipated Problems (UP)

The Office for Human Research Protections (OHRP) considers unanticipated problems (UPs)(may include a data breach) involving risks to participants or others to include, in general, any incident, experience, or outcome that meets all of the following criteria:

- Unexpected in terms of nature, severity, or frequency given (a) the research procedures that are described in the protocol-related documents, such as the Institutional Review Board (IRB)-approved research protocol and informed consent document; and (b) the characteristics of the participant population being studied:
- Related or possibly related to participation in the research ("possibly related" means there is a reasonable possibility that the incident, experience, or outcome may have been caused by the procedures involved in the research); and

 Suggests that the research places participants or others at a greater risk of harm (including physical, psychological, economic, or social harm) than was previously known or recognized.

Version Date: 11/16/2021

 This definition could include an unanticipated adverse device effect. Please refer to section 9.2.1 for the definition of an unanticipated adverse device effect.

9.5.2 Unanticipated Problem Reporting

Site Reporting Requirements

- UPs that are SAEs will be reported in accordance with the guidelines for SAE reporting.
- UPs that are not adverse events, protocol deviations or data breaches (see section 9.6 for reporting for data breaches)
 - Report to the UVA CC within 2 calendar days from the time the study team receives knowledge of the event.
 - Non- relying sites: Report to your IRB of record in accordance with your IRB guidelines.
 - Relying sites (use the UVA IRB-HSR as the IRB of record): the UVA CC will report to the UVA IRB-HSR in accordance with the guidelines.
 - UVA Site: report to the UVA IRB-HSR in accordance with the guidelines see sponsor reporting requirements.

UVA Reporting Guidelines

- Report UPs that are not adverse events or protocol deviations to the UVA IRB-HSR within 7 calendar days from the time the study team receives knowledge of the event. Report using the Unanticipated Problem Report form.
- Report to Brachyfoam within 48 hours of UVA CC's awareness of the event. To do so, email *[contact]*.
- All UPs will be reported to appropriate institutional officials (as required by an institution's written reporting procedures), the supporting agency head (or designee), and the Office for Human Research Protections (OHRP) in accordance with institutional policies.

An unanticipated device effect may also qualify as an unanticipated problem. Please follow the guidelines for reporting UADEs in *section 9.2.2*.

9.5.3 Reporting Unanticipated Problems to Participants

If during the course of the study there is an unanticipated problem that affects current or past participants, affected participants will be contacted if needed.

9.6 Data Breach

9.6.1 Definition of Data Breach

An unauthorized acquisition, access, or use of protected health information (PHI) that compromises the security or privacy of such information.

9.6.2 Reporting a Data Breach

Site Reporting Requirements

 Report to the UVA CC within 24 hours from the time the study team receives knowledge of the event.

Version Date: 11/16/2021

- Non- relying sites: Report to your IRB of record in accordance with your IRB guidelines.
- Relying sites (use the UVA IRB-HSR as the IRB of record): the UVA CC will report to the UVA IRB-HSR in accordance with the guidelines.
- UVA Site: report to the UVA IRB-HSR in accordance with the guidelines.

UVA Reporting Guidelines

- Report to the UVA Corporate Compliance and Privacy Office as soon as possible and no later than 24 hours from the time the incident is identified. Report by telephone.
- Report to ITC if the breach involves electronic data. Report as soon as possible and no later than 24 hours from the time the incident is identified. Refer to the following for details: http://security.virginia.edu/report-information-security-incident.
- Report to UVA police if the breach includes such things as stolen computers.
 Report by telephone.
- Report to Brachyfoam within 48 hours of UVA CC's awareness of the event. To do so, email *[contact]*.

9.7 Protocol Deviation

9.7.1 Definition of Protocol Deviation

A protocol deviation is defined as any change, deviation, or departure from the study design or procedures of a research project that is NOT approved by the institution's IRB prior to its initiation or implementation, OR deviation from standard operating procedures, Good Clinical Practices (GCPs), federal, state or local regulations. Protocol violations may or may not be under the control of the study team or UVA staff. These protocol violations may be major or minor violations.

9.7.2 Protocol Exception

Protocol exceptions are circumstances in which the investigator wishes to deviate from eligibility criteria or one or more of the specific procedures called for in a research plan. Unlike modifications that apply to all subsequent subjects in the research, a protocol/research plan exception only applies to a specific subject or group of subjects. Exceptions are planned, and the investigator gets approval from the lead site ahead of time. Such a request should be rare and justified in terms of serving the best interests of the potential study participant. The Lead site will receive permission from the DSMB for any exceptions at the Lead site.

9.7.3 Reporting of a Protocol Deviation or Exception

It is the responsibility of the site investigator to use continuous vigilance to identify and report deviations. All deviations must be addressed in study source documents.

Version Date: 11/16/2021

Site Reporting Requirements: Major Deviations Only

- Report to the UVA CC within 4 calendar days from the time the study team receives knowledge of the event.
- Non- relying sites: Report to your IRB of record in accordance with your IRB guidelines.
- Relying sites (use the UVA IRB-HSR as the IRB of record): the UVA CC will report
 to the UVA IRB-HSR in accordance with the guidelines—see sponsor reporting
 requirements.
- UVA Site: report to the UVA IRB-HSR in accordance with the guidelines—see sponsor reporting requirements.

UVA Reporting Guidelines

- Report to the UVA IRB-HSR major deviations within 7 calendar days from the time the study team received knowledge of the event. Report using the Protocol Deviation and Protocol Exception Reporting Form.
- Report major deviations to Brachyfoam within 7 calendar days of UVA CC's awareness of the event.
- Minor deviations do not need to be reported to the UVA IRB-HSR. Refer to the Study Reference Manual for instructions on recording minor deviations.

9.8 Participant Withdrawals/Dropouts Prior to Study Completion

Participants who withdraw consent and those dropping out of the study secondary to an AE will be reported to the UVA IRB yearly on the IRB continuation form.

10 STATISTICAL CONSIDERATIONS

10.1 Design

This is a two-center, stratified and randomized, four period, two arm crossover, noninferiority trial to demonstrate that BrachyGel Vaginal Hydrogel Packing System (hydrogel) is non-inferior to standard method vaginal packing (standard) in dose thresholds for D2cc (in Gy) for rectum and bladder by more than a non-inferiority margin of δ =1 Gy. Outcomes will be measured after each of 5 treatment fractions with results from the 1st fraction serving as the baseline measurement for each participant. D2cc measurements within organs varies between fractions as well as by participants, thus, each participant will receive both types of vaginal packing with order of packing type being chosen at random. Specifically, all participants will receive the standard method during the 1st fraction and then either sequence A (standard-hydrogel-standard-hydrogel) or sequence B (hydrogelstandard-hydrogel-standard) chosen at random, for the remaining four fractions. It is possible for participants to require less therapy during the final fraction (ie maximum therapy has been applied to the tumor), thus, the choice of ordering is limited to these two orderings to ensure that both packing types are administered to each participant with the primary assessment based upon fraction 2 and 3 data (ie, a two period, two treatment crossover).

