10.4 Sample Size and Accrual

For this crossover study the primary comparison is based upon the 2x2 initial crossover portion. The primary endpoint is the difference of D2cc dosimetry measurements between periods 1 and 2 (fractions 2 and 3) for sequence arm A and sequence arm B based upon a two-sample comparison of the mean difference to the non-inferiority margin. Data from 51 patients treated at UVA with fraction 2 and 3 information, reported overall in Romano et al 2018¹⁹, with standard packing resulted in a mean (standard deviation) of 0.12 (1.56) and 0.10 (0.92) D2cc for the difference for bladder and rectal dosimetry, respectively. The

width of the 95% CI for the mean difference was 0.9 and 0.5 for bladder and rectal dosimetry, respectively. Based upon these measurements and clinical judgement, a non-inferiority margin of δ =(0.12+1.56=1.68) was chosen for this study.

Version Date: 11/16/2021

Justification for the sample size is based upon obtaining sufficient accrual to test the primary hypothesis that use of the hydrogel vaginal packing is non-inferior to standard packing methods in 1) bladder and 2) rectal dosimetry by more than a non-inferiority margin. Let $diff_A$ and $diff_B$ denote the differences between fractions.

The primary hypothesis to be tested is H_o : μ_{diffA} - μ_{diffB} $\geq \delta$ versus H_a : μ_{diffA} - μ_{diffB} $< \delta$, where the non-inferiority margin, δ =1.68, *each* for bladder and rectal, with a one-sided 2.5% level t-test. A sample size of 20 evaluable cervical cancer participants per arm achieves 94% power to detect non-inferiority using a one-sided t-test when the margin of non-inferiority is 1.68, the true difference between the means and the reference (standard) value is 0.12, and the assume population standard deviation is 1.56. Power is 96% if one uses the estimates for rectal dosimetry.

Adjusting for participants not satisfying the evaluable criteria (*section 10.3.1*), it is estimated that approximately 57 cervical cancer participants will need to be accrued to the study in order to test the primary study hypothesis. Each site may allow up to 10 oncologist and 4 physicists/dosimetrist to participate in completing the Physician and Physicist Assessments.

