10.6 Analyses

Two main sets of analyses for all endpoints are proposed. The first limits assessment to data from periods 1 and 2, and the second uses data from all periods. The first set will summarize data based upon differences between period endpoints, with comparisons by arm. The second will employ repeated measure models to estimate period effects.

For fractions 2-5, adverse events will be summarized by frequency and severity and packing type. For the ordinal measures, mean differences and 95% confidence intervals for the difference will be calculated by packing type. Repeated measure models will be used to describe treatment' effects over time and F-tests will be used to assess period affects. Graphical methods will aid in assessing model assumptions.

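### Sections 10.1 and 10.4 give two non-inferiority margins (1 Gy and 1.68) that agree on no scale the plan supports, so some results pass under one and fail under the other

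*Combined protocol and SAP*

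**What the plan says.** Section 10.1 (Design) describes a crossover trial to show non-inferiority in D2cc "for rectum and bladder by more than a non-inferiority margin of δ =1 Gy".

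Section 10.4 (Sample Size and Accrual) takes historical fraction 2 and 3 differences from 51 patients with standard packing: mean 0.12 (SD 1.56) for bladder and 0.10 (SD 0.92) for rectum. From these and clinical judgement, "a non-inferiority margin of δ =(0.12+1.56=1.68) was chosen for this study". The hypothesis then sets μ_diffA − μ_diffB against 1.68, "each* for bladder and rectal, with a one-sided 2.5% level t-test". The quantities diffA and diffB are said only to "denote the differences between fractions", with no direction of subtraction. The stated power with 20 evaluable per arm is 94% for bladder, and for rectum: "Power is 96% if one uses the estimates for rectal dosimetry".

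Section 10.6 (Analyses) gives no margin: "The first set will summarize data based upon differences between period endpoints, with comparisons by arm". In the amendment history (13.5), the only listed change to section 10.4 is the enrolment goal, from 70 to 57. Both margins therefore stand in the current version.

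**The concern.** In a non-inferiority trial the margin decides the yes/no answer. Here the same primary comparison has two margins, and no rule says which prevails.

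The conflict would be harmless if the two were one threshold on two scales, for example the packing effect and the between-arm contrast of period differences. If they are not, some results count as non-inferior under one section and not under the other. The trial is also unblinded (section 6.4), so a threshold left open could be settled after the data are seen.

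A secondary question is where the rectal margin comes from. The value 1.68 is the bladder mean plus the bladder SD, carried over to the rectum.

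**Working it through.** **Inputs.** From 10.1: margin 1 Gy; in fractions 2 and 3, arm A is standard then hydrogel and arm B the reverse. From 10.4: margin 1.68; 20 evaluable per arm; one-sided 2.5% two-sample t-test; true difference 0.12 and SD 1.56 (bladder); 0.10 and 0.92 (rectum); accrual 57.

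**1. The plan's own power figures.** Power is P(T > t₀.₉₇₅,₃₈), where T is noncentral t with 38 df and noncentrality (margin − true contrast) / (SD·√(2/20)), and t₀.₉₇₅,₃₈ = 2.0244.
- Bladder: (1.68 − 0.12) / (1.56 × 0.3162) = 1.56/0.4933 = 3.162, which gives 86.9%. The stated 94% does not reproduce. A one-sided 5% level gives 92.8%.
- Rectum: (1.68 − 0.10) / (0.92 × 0.3162) = 1.58/0.2909 = 5.431, which gives 99.96%. The stated 96% does not reproduce. A margin of 1 gives 85.4%, so that does not explain it either. No particular rectal margin can be inferred from the 96%.

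**2. Can a scale change reconcile the margins?** Let τ be the packing effect (hydrogel minus standard) and π the fraction 3 minus fraction 2 period effect, with no carryover. Taking each difference as fraction 3 minus fraction 2:
- diffA = π + τ
- diffB = π − τ
- diffA − diffB = 2τ

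The direction is an assumption, because 10.4 does not state it. The reverse subtraction gives −2τ, and hydrogel minus standard within each arm cancels τ. Fraction 3 minus fraction 2 is the only one of these three under which the written alternative (contrast below δ) tests that hydrogel does not raise the dose too far.

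| Scale | 10.1 margin | 10.4 margin |
|---|---|---|
| Both on the contrast | 1 | 1.68 |
| 10.1 on packing effect, shown as contrast | 2 | 1.68 |
| 10.1 on packing effect, shown as packing effect | 1 | 1.68/2 = 0.84 |

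Other divisors also fail: 1.68/√2 = 1.19 and 1.68/1.56 = 1.08.

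**3. Range of results in dispute.** Non-inferiority is shown if the estimate of diffA − diffB plus the half-width is below the margin. The half-width is 2.0244·SD·√(2/20), with the observed SD set to the planning SD.

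| | Half-width | Cut-off at 1 | Cut-off at 1.68 | Cut-off at 2 |
|---|---|---|---|---|
| Bladder | 0.999 | 0.00 | 0.68 | 1.00 |
| Rectum | 0.589 | 0.41 | 1.09 | 1.41 |

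- (a) Both margins on the contrast: bladder estimates from 0.00 to 0.68 and rectal estimates from 0.41 to 1.09 pass under 10.4 and fail under 10.1.
- (b) 1 Gy as packing effect: bladder estimates from 0.68 to 1.00 and rectal estimates from 1.09 to 1.41 pass under 10.1 and fail under 10.4.

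**4. Bladder power, 20 per arm.**

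| True contrast | Margin 1 | Margin 1.68 | Margin 2 |
|---|---|---|---|
| 0.12 | 41.2% | 86.9% | 96.0% |
| 0.24 (packing effect 0.12) | – | 81.2% | 93.5% |

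Under (a), at the planning value, the two sections give opposite bladder verdicts with probability of about 46 percentage points (86.9 − 41.2).

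**5. Source of the rectal margin.** Bladder mean plus SD is 0.12 + 1.56 = 1.68. The same sum for the rectum is 0.10 + 0.92 = 1.02.

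**The case against.** The strongest reply is that section 10.4 governs in practice. It alone contains formal hypotheses, it says its margin was chosen for the study, and it uses that value for the sample size. Section 10.1 is a design description, so an analyst would most naturally test against 1.68. That is a fair prediction, but the plan does not say so. Section 10.1 is equally current and is the only place that attaches Gy to the margin. Defaulting to 1.68 would also leave its direction and scale unstated.

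Several narrower points stand in part:
- The factor of two depends on a direction of subtraction that 10.4 does not give. This is true, but the conflict does not need it: on a common scale, 1 differs from 1.68.
- In reading (b), taking 0.12 as the packing effect is a choice. Section 10.4 places 0.12 on the tested difference, which is why the power table shows both.
- The missing unit on 1.68 is minor, since D2cc is in Gy throughout. A common margin for both organs is a stated choice, though a thinly supported one.
- A reported confidence interval on a named contrast would show what dose increase is excluded, whichever margin applied. That helps interpretation but does not settle the pass/fail verdict.

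**Conclusion.** The concern holds. The plan carries two unreconciled margins for one primary comparison, and no conversion the documents support makes them equal. Even which of the two is stricter is unknown: 1 Gy is stricter if both apply to the contrast, and 1.68 is stricter if 1 Gy means the packing effect.

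The verdict is therefore unsettled over a band of estimates 0.68 wide in the first case and 0.32 wide in the second (2 − 1.68), for each organ. The location of these bands rests on 20 evaluable per arm, observed SDs equal to the planning SDs and, for the second case, differences taken as fraction 3 minus fraction 2. The contradiction itself rests on none of these. It must be fixed before analysis.

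**What to change.** Before any analysis, state one margin per organ, in Gy, on one named scale, in identical terms in 10.1 and 10.4. The scale should be either the packing effect, or the diffA − diffB contrast with its direction of subtraction. Give the reason for the rectal value, or for one common value. Recompute the power for both organs from that margin and scale, replacing the 94% and 96%.

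The cost is wording and restated power, and depends on the choice:
- **1.68 on the contrast:** no change in numbers if 86.9% bladder power (true contrast 0.12) is acceptable. Keeping the stated 94% needs 26 evaluable per arm, within the roughly 28 per arm that 57 accrued would allow if all were evaluable. If the true packing effect is 0.12, power is 81.2% and 94% needs 30 per arm, which exceeds that.
- **1 Gy as packing effect (2 on the contrast):** no extra patients; bladder power is 96.0% at a true contrast of 0.12 and 93.5% at 0.24.
- **1 Gy on the undivided contrast:** bladder power must be restated at about 41% with 20 per arm. It would be 54.5% with 28 per arm; 80% needs 51 evaluable per arm and 90% needs 68.
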